5.0 Special Considerations

5.1 Health Insurance Portability and Accountability Act (HIPAA)

No identifiable health information will be utilized during this study.

5.2 Family Educational Rights and Privacy Act (FERPA)

N/A

5.3 Code of Federal Regulations Title 45 Part 46 (Vulnerable Populations)

Review the following guidance to ensure you have sufficient information when specific populations are included in your research study.

A. Special Populations

N/A

5.4 General Data Protection Regulation (GDPR)

N/A

5.5 NJ Access to Medical Research Act (Surrogate Consent)

N/A

6.0 Data Management Plan

6.1 Data Analysis

Treatment analysis will involve a 1-way repeated measures ANOVA. Differences will be considered significant when p values are below an alpha level of 0.05.

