1.0 Research Design

1.1 Purpose/Specific Aims

The purpose of this study is to find an alternative, low risk option for managing muscle soreness in the older adult and elderly population.

A. Objectives

This study aims to compare how the topical application of essential oils *Eucalyptus globulus* and *Mentha x piperita* impact delayed onset muscle soreness after eccentric exercises compared to one another and to control.

B. Hypotheses / Research Question(s)

It is hypothesized that application of *Eucalyptus globulus* or *Mentha x piperita* oil will reduce perceived muscle soreness in subjects compared to control.

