1.3 Research Design and Methods

This study is designed as a randomized controlled interventional study with a rolling enrollment over the course of 6 months, with each individual subject's participation spanning over 72 hours. 20 subjects will be recruited for participation. 10 subjects will be included in the *Eucalyptus globulus* intervention group, and the remaining 10 will be placed in the *Mentha x piperita* group. A blocked randomisation list will be generated using an online randomizer in order to allocate subjects to each treatment group randomly. Each subject will have one upper extremity serving as the control, and one upper extremity which receives the intervention.

A. Research Procedures

Subjects

Subjects 50 years old and above with no previous resistance training sessions within the past year will be recruited at The Manor Health and Rehabilitation, a subacute rehabilitation and long-term care facility. A verbal explanation will be provided to the potential subjects by [name] or [name] on-site at the facility, including the fact that their care at the facility will not be affected by their decision to participate or not, and if they are interested in proceeding they will be asked to complete a survey regarding the subject's demographics (gender, age, hand dominance), ensure there are no hypersensitivities to the oils being used, upper extremity injuries within 1 year, and that they have the functional capacity for exercise of 3.5 metabolic equivalents or greater based on the Duke Activity Status Index. Subjects will be required to sign a consent to participate in screening. If participants pass the screening process they will again be informed of the study and all potential risks/benefits prior to signing an informed consent to partake in research.

Materials

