Participants will be divided equally into the *Mentha x piperita* or the *Eucalyptus globulus* group. A 2% oil mixture for topical application will be made with essential oils from SunRise Aromatics diluted in fractionated coconut oil per guidelines from the RJ Buckle Clinical Aromatherapy for Health Professionals course recommendations. Physiciansupervised eccentric exercise of the elbow flexors will be performed based on an adaptation of the method described by Weber. [14] Free weight dumbbells will provide resistance. The subject will be instructed to prolong the extension aspect of the curl to be five seconds long. They will repeat this motion for 10 or more repetitions until exhaustion, either due to the participant feeling they can no longer tolerate the five second eccentric aspect of the exercise or the investigator identifying that their form has faltered. If subjects reach exhaustion after the 10 repetitions minimum, they will rest for 1 minute. If they are unable to complete 10 repetitions at this weight, the resistance will be decreased to the next lowest weight and they will continue until exhaustion. This will continue until subjects reach exhaustion with the lowest resistance weight. Immediately following exercise, the participants will have the respective oil applied topically to their left upper extremity by the investigator. Their right upper extremity will serve as the control and no essential oil will be applied. Investigators will apply the oil without any use of massage technique and to only apply very superficial pressure. This application will be repeated 8 hours after exercise, when DOMS has been known to initiate, and at 24 hours after exercise, when DOMS may begin to peak.

Subject Safety

Vital signs will be measured prior to the initiation of exercise, including temperature, heart rate, blood pressure, and oxygen saturation. A physician will be notified of any abnormalities and the subject must be medically optimized prior to exercising. All exercise will be supervised by a physician. After the intervention is applied, subjects will be directly observed for 15 minutes by a physician to ensure no immediate adverse reactions occur. Vital signs will be repeated at the end of the observation period.

Nursing staff will be on-site in their usual capacity and physicians available on-call throughout the duration of the study. Medications are available at the facility if needed for any adverse events.

B. Data Points

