Subject outcomes will be based on a self-reported visual analog scale, which has previously been shown to have validity in subjectively quantifying perceived muscle soreness and used in prior studies. [14,16]. These outcomes will be recorded by investigators for both the intervention and control upper extremity at 24, 48, and 72 hours post-exercise.

C. Study Duration

Each subject will participate in this study for 72 hours. The overall study is anticipated to take place over a six month duration.

D. Endpoints

The primary endpoint will be a self-reported perceived muscle soreness using a visual analog scale. There are no secondary endpoints.

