1.5 Sample Size Justification

We anticipate a sample size of 20 subjects, 10 subjects in the *Eucalyptus globulus* group and 10 subjects in the *Mentha x piperita* group. This is based on previous studies which have investigated interventions for perceived muscle soreness and utilized a similar sample size for a power of 80% and a 1 tailed level of significance of p<0.05. [15]

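### The planned 1-way repeated measures ANOVA has no oil-versus-oil contrast, although the objective names that comparison, and for oil versus control the use of the 24, 48 and 72 h scores is not fixed

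*Combined protocol and SAP*

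**What the plan says.** The objective (section 1.1 A) is to see how the two oils "impact delayed onset muscle soreness after eccentric exercises compared to one another and to control". The hypothesis (section 1.1 B) is narrower: either "oil will reduce perceived muscle soreness in subjects compared to control".

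The design (section 1.3) randomises 20 subjects, 10 to each oil. "Each subject will have one upper extremity serving as the control, and one upper extremity which receives the intervention". The treated side is fixed: "the participants will have the respective oil applied topically to their left upper extremity by the investigator". Soreness scores are "recorded by investigators for both the intervention and control upper extremity at 24, 48, and 72 hours post-exercise".

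The endpoint statement (section 1.3 D) is: "The primary endpoint will be a self-reported perceived muscle soreness using a visual analog scale". It names no time point and no summary over time, and there are no secondary endpoints.

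The analysis text (section 6.1) is two sentences. The first is "Treatment analysis will involve a 1-way repeated measures ANOVA"; the second sets alpha at 0.05. They do not name the factor, the handling of the three times, any contrast between oils, or the sidedness. Section 1.5 justifies the sample size by earlier studies that used "a power of 80% and a 1 tailed level of significance of p<0.05". No other section adds analysis detail.

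**The concern.** The design has three factors: oil (between subjects), arm (within subject) and time (within subject). A 1-way repeated measures ANOVA normally has one factor, and it is within subject. One of the two comparisons in the objective therefore has no term in the stated analysis.

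For the other comparison, oil versus control, the method can be applied with arm as the factor, but the plan does not say which of the three scores, or which combination of them, enters the test. This is the only analysis of the only endpoint, and section 1.6 says that subjects know which oil they receive, so a fixed analysis is one of the few safeguards left. Without it, the time summary can be chosen after the scores are seen.

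**Working it through.** **1. The plan's own figure.** The sample size of 20 cannot be reproduced, because section 1.5 gives no effect size, SD, correlation or target comparison. Back-solving with the exact noncentral t for 80% power at one-tailed 0.05 gives 0.85 SD of the arm difference for one oil (10 pairs), or 0.58 SD for both oils pooled (20 pairs). At two-sided 0.05 these become 1.00 and 0.66 SD.

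**2. Factors against the named method.**

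| Factor | Levels | Varies | Section |
|---|---|---|---|
| Oil | eucalyptus, peppermint | between subjects, 10 v 10 | 1.3 |
| Arm | treated, control | within subject | 1.3, 1.6 |
| Time | 24, 48, 72 h | within subject | 1.3 B |

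Let D be a subject's treated-arm minus control-arm score, averaged over time, with true mean dE for eucalyptus and dM for peppermint. With arm as the factor and the oils pooled, the ANOVA F equals t squared for the mean of D over 20 subjects. It tests whether (dE + dM)/2 is zero. Oil versus oil asks whether dE - dM is zero. The first quantity does not determine the second. Running the ANOVA separately in each oil group does not help either: one significant result and one non-significant result are not a test of the difference.

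**3. Size of the gap.** The documents give no SD. Assumed: 0-100 mm scale, subject SD 15, arm SD 8, residual SD r = 10 to 20 mm. The subject term cancels in D.

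SD of D = sqrt(2 x (8² + r²/3)) = sqrt(2 x 97.3) = 14.0 mm at r = 10, and sqrt(2 x 197.3) = 19.9 mm at r = 20.

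- Pooled arm test, both oils 10 mm: noncentrality 10 x sqrt(20)/SD = 3.21 to 2.25, power about 86% to 57%.
- Pooled arm test, 20 and 0 mm: the mean is still 10 mm, but the gap between oils adds to the spread of D. By simulation, about 73% to 47%.
- Between-oil contrast, 20 and 0 mm: noncentrality 20/(SD x sqrt(2/10)) = 3.21 to 2.25 on 18 df, about 86% to 57%.
- Between-oil contrast, both 10 mm: 5%.

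The pooled test gives similar answers to two situations that the objective asks to tell apart.

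**4. Oil versus control.** With arm as the factor, the times averaged and no oil effect, 20,000 simulated trials per scenario reject in 4.65-5.3%. The test is valid once the summary is fixed.

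If the summary is left open among four choices (mean, 24, 48 or 72 h), the chance of at least one two-sided p<0.05 for one oil with no effect is 14.8%, 15.4% and 15.9% at r = 10, 15 and 20. Counting only results in the hypothesised direction gives about 7-8%. With a one-tailed 0.05 test it is 13-15%. With a larger assumed arm SD of 15-20 mm, the two-sided figure is 11-15%.

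**5. Precision of the missing contrast.** At 10 v 10 and two-sided 0.05, 80% power needs 1.32 SD of D, that is 18.5 to 26.3 mm under the assumed SDs. The 95% CI half-width is 2.101 x sqrt(2/10) = 0.94 SD, about 13 to 19 mm.

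**The case against.** The strongest reply is that a one-way treatment factor with three levels (eucalyptus, peppermint, control) and subjects as incomplete blocks does yield an oil-versus-oil test. Checked on one data set, it gives the same t on 18 df as a two-sample test of the arm differences, and the independent variables in section 1.6 are compatible with it. This stands as far as it goes. A reader might infer that the trial cannot compare the oils, and that would be wrong: the data can support the comparison. But section 6.1 does not describe this layout or any between-oil contrast.

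Second, the hypothesis covers only oil versus control, for which the arm test is sound. This also stands: the missing contrast is a gap against the objective, not the hypothesis.

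Third, a reader might infer a planned search over time points, or a type I error that is actually 15% or more. The documents do not support that. No section plans a search, and the figure only measures the room that the wording leaves. Counting both oils and pooled versions would raise it, but that mixes in ordinary two-oil multiplicity, and the hypothesis and the 10-per-group sizing favour a test for each oil.

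Fourth, one might suppose that time is the ANOVA factor, so that the test would pick up the natural course of soreness. Section 6.1 speaks of treatment analysis, which points to arm.

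**Conclusion.** The point holds in two parts.

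The structural part depends on no assumed number: the method in section 6.1, as normally run, contains no oil-versus-oil contrast, the objective asks for one, and a pooled arm test does not supply it.

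The second part is under-specification. Oil versus control has a valid test, but its time summary is not fixed in section 6.1 or in the endpoint statement. The 15-16% for one oil rests on the assumed SDs, counts both directions, and supposes that all four summaries are tried.

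It does not follow that the oils cannot be compared, or that the arm test is invalid. Because this is the sole analysis of the sole endpoint, the text should be settled before results are seen.

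**What to change.** Replace section 6.1 with text such as:

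> For each subject the outcome is treated-arm VAS minus control-arm VAS, summarised over 24, 48 and 72 h by one summary named in advance (for example the mean). Each oil versus control is tested within that oil group on this difference. Oil versus oil is a two-sample comparison of the differences (equivalently the oil-by-arm term of a mixed ANOVA), reported with a 95% CI. Per-time results are descriptive.

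The new text should also:

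- say whether the two oil-versus-control tests are adjusted for multiplicity;
- state the sidedness and reconcile it with section 1.5, since the usual ANOVA F is non-directional.

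A linear mixed model with a small-sample df method is an acceptable alternative, not a requirement.

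Two related passages bear on what the contrast means. Sections 1.3 and 1.6 leave the control arm without essential oil or without treatment, whereas the timetable in section 1.10 has control oils applied; these must be reconciled. Treated versus control is also left versus right (section 1.3), which no analysis can separate and which should be stated as a limitation.

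The cost is wording only, with no new data, but there are two downsides:

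- Oil versus oil remains imprecise at 10 v 10 and should be reported as an estimate.
- A two-sided or adjusted oil-versus-control test has less power than the one-tailed test cited in section 1.5. At 0.85 SD with 10 pairs (noncentrality 0.853 x sqrt(10) = 2.70, 9 df), power falls from 80% at one-tailed 0.05 to about 67% at two-sided 0.05 and 53% at two-sided 0.025. Estimating the variance from both groups (18 df) gives about 72% and 60%.

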1.9 Data Collection

A. Primary Data Collection

Location: Data collection will occur at the Manor Health and Rehabilitation Center ([name]). Permission has been granted by the director of this facility and by authorities with CentraState Healthcare System, which the Manor is owned by.

- Process of Data Collection: The investigators will oversee the collection of data in-person at the facility. Only Rutgers study staff will be involved in any research roles. Staff at the Manor Health and Rehabilitation will not be involved in the collection of data or treatment of subjects pertaining to this study, but will maintain their usual roles at the study site throughout the duration of this investigation.
- Timing and Frequency: Data collection will occur at the beginning of a subject's participation in order to collect demographic information, and then at 24, 48, and 72 hours following exercise to survey their perceived muscle soreness.
- Procedures for Audio/Visual Recording: There will be no recording of subjects.
- Study Instruments: Recruited subjects will complete a survey to collect demographic data, medical history, and allergies. Subjects will identify their perceived muscle soreness using a self-reported visual analog. They will complete this for both the control and intervention arm at 24, 48, and 72 hours post-exercise.
- Ethnographic Studies, Interviews, Or Observation: There will be no interviews or observational aspect to this study.
- Subject Identifiers: Each subject will be assigned to a random number associated with their name that will be stored in a password protected file on a secure drive. In a separate, also password protected, file the collected data will be stored with the associated subject's number
- B. Secondary Data Collection: No secondary data collection will occur.

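### Section 6.1 names a 1-way repeated measures ANOVA for six readings per subject without fixing the factor or error term; if all six readings enter, the oil-versus-control test can miss its 5% level in either direction

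*Combined protocol and SAP*

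**What the plan says.** The analysis plan is two sentences in section 6.1: "Treatment analysis will involve a 1-way repeated measures ANOVA", and "Differences will be considered significant when p values are below an alpha level of 0.05". They do not name the factor, its levels, the error term, the handling of visits, a sphericity correction or the sidedness.

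The design has more structure than one factor. Section 1.3 states: "Each subject will have one upper extremity serving as the control, and one upper extremity which receives the intervention". Section 1.9 says of the soreness scale: "They will complete this for both the control and intervention arm at 24, 48, and 72 hours post-exercise". So arm (2 levels) and visit (3 levels) vary within subject, and oil varies between two groups of ten. The hypothesis in section 1.1 is that either oil lowers soreness relative to control, and the objectives add a comparison of the two oils. The endpoint in section 1.3 D names neither a visit nor a summary over visits. Section 1.5 refers to earlier studies that "utilized a similar sample size for a power of 80% and a 1 tailed level of significance of p<0.05".

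**The concern.** A one-factor model can use all six readings only if they become six levels of one factor, or if the three visits are entered as replicates of each arm. Both layouts leave a single residual, and oil versus control is tested against it.

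That is the wrong yardstick when an arm keeps its own level of soreness. Exercise takes place once, and the same two arms are then scored three times. An arm that is sorer at 24 hours for reasons unrelated to oil may still be sorer at 48 and 72 hours, so a subject's three left-minus-right differences do not carry three subjects' worth of information. The proper error for oil versus control is the subject-by-arm variation, on n-1 df. The pooled residual averages it with subject-by-visit variation and reading-to-reading noise.

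The trial's only hypothesis rests on this comparison. Because section 6.1 leaves the layout open, it could also be chosen after the data are seen.

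**Working it through.** **Inputs from the documents.** 2 arms x 3 visits = 6 readings per subject (sections 1.3 and 1.9); 10 subjects per oil, 20 in all (section 1.5); alpha 0.05 (section 6.1).

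**Assumed.** The documents give no variance or correlation. Let b be the variance of a persistent arm-within-subject effect, c the subject-by-visit variance and e the residual variance.

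**Plan's own figure.** The only figure to reproduce on this point is the 5% level. The sample size cannot be re-derived, because section 1.5 gives no effect size or SD.

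**Step 1, degrees of freedom.** The six-level layout has 5(n-1) residual df: 45 for n = 10 and 95 for n = 20. The subject-by-arm error has n-1: 9 and 19.

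**Step 2, expected mean squares.** Per n-1 df: subject-by-arm is 3b + e (1 part), subject-by-visit is 2c + e (2 parts), and the three-way term is e (2 parts). Pooled:

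[(3b + e) + 2(2c + e) + 2e] / 5 = (3b + 4c + 5e) / 5

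**Step 3, true variance over variance used.**

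ratio = 5(3b + e) / (3b + 4c + 5e)

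This exceeds 1 when 15b + 5e > 3b + 4c + 5e, that is, when b > c/3. Above that threshold the p-value is too small; below it, too large.

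**Step 4, actual error.** Simulation with no oil effect, n = 10, two-sided nominal 5%, testing the oil-versus-control contrast on the pooled residual:

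| c | b | ratio | actual error |
|---|---|---|---|
| e | 0.5e | 12.5/10.5 = 1.19 | about 7% |
| e | e | 20/12 = 1.67 | about 13% |
| e | 2e | 35/15 = 2.33 | 19-20% |
| 0.5e | 0.5e | 12.5/8.5 = 1.47 | 10-11% |
| 0.5e | e | 20/10 = 2.00 | about 16% |
| 0.5e | 2e | 35/13 = 2.69 | 22-23% |
| 2e | 0.5e | 12.5/14.5 = 0.86 | about 4% |
| 3e | e | 20/20 = 1.00 | about 5% |
| e | 0 | 5/9 = 0.56 | about 1% |

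Hand check of the second row: the two-sided 5% critical t on 45 df is 2.014, and 2.014/√1.67 = 1.56, which a normal table turns into about 12%. Results at n = 20 are nearly the same.

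**Step 5, other layouts.** With c = 0 and correlations of 0.3, 0.5 and 0.9 between a subject's differences at two visits, the six-level contrast gives about 14%, 21% and 35%, and the replicate layout about 14%, 22% and 37%. With correlation 0, both give about 5%. The uncorrected omnibus F over the six cells runs at about 6-8% in the six settings with c = e or 0.5e and b from 0.5e to 2e.

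**Step 6, one value per subject.** A t test on each subject's mean left-minus-right difference gives about 5% in every setting (4.6% to 5.1% in the correlation runs).

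**The case against.** The strongest reply is that section 6.1 never says six readings will share one factor. If arm is the factor, at one visit or on the visit mean, the error term is subject-by-arm, the analysis equals a paired t test, and the 5% level holds. This stands. A reader might infer that any 1-way repeated measures ANOVA has the pooled-error fault, or that this trial's p-values will be wrong; the text supports neither. What remains is that the valid layout needs an averaging or visit-selection step that the plan does not give.

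A second reply is that the direction is unknown. This also stands. A reader might infer that the p-value is usually too small, but that requires b > c/3, and the documents give no variances. Section 1.2 puts the onset of soreness at 8 to 24 hours and the peak at 24 to 48 hours. Subjects may therefore differ in time course, which raises c and can make the test conservative.

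A third reply is that a six-cell ANOVA produces the omnibus F first, and its inflation is modest. This is correct, but the omnibus F asks whether any of six arm-visit means differ, including change over time. It does not answer the hypothesis in section 1.1; the contrast does.

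**Conclusion.** The point holds as a conditional one. The named method fits this design only with a step that the plan omits. If all six readings enter a one-factor model, oil versus control is tested on a residual with 45 df for ten subjects instead of 9. Its true two-sided error at nominal 5% then lies between about 1% and about 22-23% over the b, c and e grid. With no subject-by-visit variance and a correlation of 0.9 between visits it reaches about 35%.

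All these figures rest on assumed variances, so they show a range and are not a forecast. They are two-sided. Section 1.5 speaks of one tail and section 6.1 is silent, but the same variance ratio governs either choice. The direction is too small when b > c/3 and too large when b < c/3. A test on one averaged difference per subject avoids the problem in every setting tried.

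**What to change.** In section 6.1, replace the ANOVA sentence with the following in substance:

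- For each subject, compute the mean over 24, 48 and 72 hours of the left-minus-right VAS difference.
- Test oil versus control within each oil group by a one-sample t test on these values, with n-1 df.
- Compare the two oils by a two-sample t test on the same values.
- State whether the tests are one- or two-sided, consistently with section 1.5.
- Apply the Greenhouse-Geisser correction to any test across visits.

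The three-visit mean is one choice of summary. A single named visit would also give a valid error term, provided it is fixed in advance.

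If all six readings are modelled instead, include random effects for subject, subject-by-arm and subject-by-visit, and keep the arm test on its subject-by-arm error even when that variance is estimated at zero. Omitting the subject-by-visit term can bring the fault back. In a check at n = 10 with c = e, a model with only subject and arm-within-subject effects fell back to the pooled residual in 92% of trials when b = 0 (actual error 1.1%) and in 63% when b = 0.25e (2.9%).

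The cost is wording only, with no new data or visits. Error df fall from 45 to 9 per oil group, and p-values may become less favourable.

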4.3 Number of Subjects

A. Total Number of Subjects

We anticipate enrolling 20 subjects to participate, 10 in the *Mentha x piperita* group and 10 in the *Eucalyptus globulus* group.

B. Total Number of Subjects If Multicenter Study

N/A

C. Feasibility

It is feasible to enroll this number of subjects given there is a consistent population of residents within this facility that would meet the age criteria and, after discussion with physicians at this facility, would also meet the criteria for exercise clearance. The nature of the facility also allows for a continuous influx of patients to the subacute rehabilitation facility, which will allow for rolling enrollment into our study.

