4.4 Consent Procedures

A. Consent Process

Location of Consent Process

The consent process will take place at the Manor Health and Rehabilitation facility.

Ongoing Consent

N/A

Individual Roles for Researchers Involved in Consent

Co-investigator [name] will obtain consent from participants. The principal investigator, [name], will be available to answer any questions or concerns from potential subjects if needed.

Consent Discussion Duration

Ten minutes of time will be allotted to discuss informed consent. Should the subject require any clarification or a longer timeframe, accommodations will be made.

Coercion or Undue Influence

Subjects will be informed this is an optional study and their medical care at the facility will not be influenced by their decision to participate or not. Subjects will be able to voice any concerns or questions they may have. Subjects will be able to leave the study at any point should they choose.

Subject Understanding

Subjects will be asked to repeat back what their role in the study would be. They will verbalize understanding prior to signing any consent forms.

B. Waiver or Alteration of Consent Process

N/A

C. Documentation of Consent

Documenting Consent

All subjects will sign a form of informed consent. They will keep a copy and another copy will be stored in a secure file which only the research staff has access to.

Waiver of Documentation Of Consent (i.e., will not obtain subject's signature)

N/A

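### If visit is the within-subject factor, the repeated measures ANOVA in 6.1 excludes any subject with one missed VAS visit; a mixed model would use every reading collected

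*Combined protocol and SAP*

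**What the plan says.** Section 6.1 (Data Analysis) consists of two sentences: "Treatment analysis will involve a 1-way repeated measures ANOVA" and "Differences will be considered significant when p values are below an alpha level of 0.05". It does not name the within-subject factor, an analysis set or a way of handling missing readings.

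Under 1.3 (Data Points) and 1.9, each subject rates both arms at 24, 48 and 72 hours, which makes three visits and six ratings. On numbers, 1.3 says "20 subjects will be recruited for participation", split 10 and 10 between the oils. Section 1.5 justifies this by reference to earlier work that "utilized a similar sample size for a power of 80% and a 1 tailed level of significance of p<0.05". It adds nothing for loss to follow-up.

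The documents foresee incomplete follow-up. Section 4.4 says "Subjects will be able to leave the study at any point should they choose". Section 4.7 urges subjects to stop if they feel harmed by the exercise, and lets them withhold information they are uneasy about giving. On how readings are obtained, 1.9 says "The investigators will oversee the collection of data in-person at the facility". The residents are a mix of subacute rehabilitation and long-term care patients, and 4.3 relies on "a continuous influx of patients to the subacute rehabilitation facility" for recruitment.

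**The concern.** A classical repeated measures ANOVA across visits works on complete subjects only. A subject who gives VAS readings at 24 and 48 h and is then lost contributes nothing, not even to the two visits that were recorded. With 10 subjects per oil and no reserve, each exclusion removes a tenth of a group.

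Two things are at stake. The first is precision: readings already collected are thrown away. The second is selection: if those who leave are the sorest, the complete subjects are no longer a fair picture of those randomised. An equally accessible method avoids the first problem and eases the second.

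**Working it through.** **The plan's own figure.** The 20 subjects cannot be reproduced, because 1.5 states no effect size or standard deviation. Solving backwards at 80% power, a paired one-sided test at 0.05 with 10 subjects detects a standardised difference of 0.85 (1.00 two-sided). This only shows that 10 per oil suits large effects.

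**Inputs.** From the documents: 3 visits, 10 subjects per oil. Assumed: a share q of visits missing (5%, 10% or 15%), both arms missing together, and a between-visit correlation ρ of 0.5 for the arm difference.

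**Subjects excluded and ratings discarded, independent misses, q = 10%.**
- Complete subjects: (1 − q)³ = 0.9³ = 0.729, or 7.3 of 10. Excluded: 27.1%.
- Ratings collected: 90% of those planned.
- Collected but discarded: 90% − 72.9% = 17.1% of planned, and 17.1/90 = 19.0% of collected.

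**Precision of the mean arm difference over the three visits.** A subject with k visits carries information k / [1 + (k − 1)ρ]. At ρ = 0.5 this is 1.5 for k = 3, 1.333 for k = 2 and 1 for k = 1. When misses are independent, all visits are equally affected, so these can be summed over the missing patterns:

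0.729 × 1.5 + 3 × 0.081 × 1.333 + 3 × 0.009 × 1 = 1.0935 + 0.324 + 0.027 = 1.4445.

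- All-available analysis: 1.4445 / 1.5 = 0.963 of full information, or 9.6 subject-equivalents of 10.
- Complete subjects only: 0.729, or 7.3.
- Variance ratio: 0.963 / 0.729 = 1.32.

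**Permanent dropout.** If a share q of those remaining leaves before each visit, the patterns at q = 10% are 0.729 complete, 0.081 with two visits, 0.09 with one and 0.1 with none. Ratings collected: (0.9 + 0.81 + 0.729)/3 = 81.3% of planned. Discarded: 81.3% − 72.9% = 8.4% of planned, or 10.3% of collected. The visits are now unequally affected, so the variance of the mean over visits comes from inverting the summed 3 × 3 information matrix. This gives 8.6 subject-equivalents against 7.3, a ratio of 1.17.

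| q | Complete of 10 | Ratio, independent misses | Ratio, permanent dropout |
|---|---|---|---|
| 5% | 8.6 | 1.15 | 1.08 |
| 10% | 7.3 | 1.32 | 1.17 |
| 15% | 6.1 | 1.53 | 1.28 |

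**Sensitivity.** At q = 10%, moving ρ from 0 to 0.9 changes the ratio from 1.23 to 1.36 for independent misses and from 1.11 to 1.22 for permanent dropout. If 10% leave only after the 48 h reading, there are 9.0 complete subjects against 9.9 equivalents, a ratio of 1.10. If the same subjects miss all three visits, no collected reading is wasted and the ratio is 1.

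**The case against.** The strongest reply is that 6.1 does not say what the single factor is. If it is arm (oil against control), tested visit by visit, a missed 72 h reading costs only the 72 h comparison. This stands: exclusion across visits is a property of one reading of the sentence, not a rule the plan states.

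The second reply is that little may go missing. Follow-up lasts 72 hours, subjects are residents, some of them in long-term care, and the investigators collect the VAS themselves. The remark on patient influx in 4.3 concerns recruitment; it gives no length of stay and does not show that anyone is discharged within three days. This also stands, and it is why the missing rate can only be an assumption.

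Three stronger readings are tempting and should be resisted.
- A reader might infer that a quarter of the data is wasted at 10% missing. The 27% counts subjects excluded and includes ratings never collected, which no analysis can recover. The waste is 19% of collected ratings under independent misses, and about 10% if subjects leave for good, which is the mechanism the withdrawal clause suggests.
- A reader might infer that the ANOVA costs the fall in power from 10 subjects to 7 (80% to 64% one-sided, 60% two-sided). That comparison is with full data, not with the mixed model, and it rests on an effect size chosen to give 80% at 10. The documents state none, and only 1.5 says one-tailed.
- A reader might infer that a mixed model cures selection. It does so only under missing at random. If subjects leave because of soreness that was never recorded, it is biased too.

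**Conclusion.** The point holds as a modest improvement, on condition that visit is the within-subject factor. The named method would then exclude every subject with an incomplete series, in a trial that permits withdrawal at will and has no spare subjects. At assumed rates of 5% to 15% and a correlation of 0.5, the variance penalty against an all-available analysis is 1.15 to 1.53 for independent misses and 1.08 to 1.28 for permanent dropout. It shrinks towards 1 if few subjects are lost, or if the same subjects miss every visit. Nothing in the documents fixes the rate or the pattern, so no single figure should be presented as the trial's expected loss.

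**What to change.** In 6.1, replace the ANOVA with a linear mixed model on the oil-arm minus control-arm VAS difference at each visit. Include fixed effects for oil, time and oil-by-time, a subject random effect and small-sample degrees of freedom, and state that every available reading is used. The mean difference within each oil answers the comparison with control in 1.1, and the oil terms answer the comparison between oils. In 1.9 and 1.10, add a final VAS for both arms, taken when a subject leaves early.

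The cost is a few sentences, standard software and one short rating at exit, with no extra subjects. The model is slightly more complex. Section 6.1 should also say that it relies on missing at random, so bias from the sorest subjects leaving is reduced rather than removed; the exit rating helps because it records soreness at the point of leaving.
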